8.3.1 GENERAL APPROACH

At each time of measurement, descriptive statistics and measures of association will be used to summarize demographic characteristics and outcome measures. The analysis will also include graphical and statistical analysis of outlying observations and distributional characteristics of variables. Differences in outcomes of interest between the control and HABITS will be assessed by t-test of equal means and Chi-square test of equal proportions for continuous, ordinal, and categorical values, respectively. Primary and secondary outcomes will be assessed using mixed regression models with home visitors as a random effect with adjustment for relevant demographic information and other measured covariates.

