8.2 SAMPLE SIZE DETERMINATION

The power analysis is prepared for comparing means of weight change from baseline to 12-months between the control and HABITS study arms. A sample size of 59 dyads per group, total of 118 dyads, will have 80% power to detect that mean of weight change in the control is 0.53 standard deviation

apart from that in HABITS by performing two-sided t-test of equal means at $\alpha=0.05$. Since participants will be nested in 18 home visitors, the unadjusted calculated sample size must be further increased by an inflation factor to account for clustering due to home visitors. The inflation factor is given by the following equation: $IF = [1 + (m - 1) p]$, where m represents the number of participants per home visitor, and p represents the intraclass correlation coefficient (ICC), the ratio of between-home visitors and total variability. In this study, we assume ICC is 0.01 consistent with typical values of ICC in community-based studies.⁸⁶ By considering a 15% attrition rate between baseline and 12-month follow-up, the required total sample size is 140 (70 dyads per group). If ICC is weaker or attrition rate is smaller than we expected, we will have stronger power to detect the same difference of means.

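### The 80% power rests on a dyad-level t-test, but arms are compared across 18 home visitors; with 16 degrees of freedom power is about 75% (140 enrolled) or 77% (148), and no small-sample method is named

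*Combined protocol and SAP*

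**What the plan says.** Section 8.2 powers the comparison of mean weight change to 12 months. It states: "A sample size of 59 dyads per group, total of 118 dyads, will have 80% power to detect" a difference of 0.53 SD, tested at a two-sided 0.05 level by an ordinary t-test of two means. It then acknowledges clustering ("Since participants will be nested in 18 home visitors") and says that "the unadjusted calculated sample size must be further increased by an inflation factor to account for clustering due to home visitors". The factor is 1 + (m − 1) × ICC, with the ICC assumed to be 0.01. After 15% attrition the section arrives at 140 dyads, 70 per group. The synopsis (1.1) gives 148.

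Sections 3.1 and 5.2 randomise home visitors: 18 in total, 9 to each arm. For the analysis, 8.3.1 states: "Primary and secondary outcomes will be assessed using mixed regression models with home visitors as a random effect", with covariate adjustment; 8.3, 8.3.2 and 8.3.3 follow the same approach. None of these sections says how degrees of freedom for the arm effect are obtained, and 8.2 makes no allowance for the small number of clusters.

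**The concern.** Every family of a given home visitor is in the same arm, so the arm effect is estimated from differences between visitors. The design effect enlarges the variance of that contrast. It does not change the reference distribution, which has 18 − 2 = 16 degrees of freedom when the between-visitor variance has to be estimated. The two-sided 5% critical value is 2.120 at 16 degrees of freedom and 1.981 at 116. A calculation that keeps the second value overstates power.

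The analysis side has the matching gap. With no method named, the degrees of freedom given to the arm effect depend on how the model is coded, and they could be residual (dyad-level). That leaves open a choice that could decide a borderline result against the 0.05 rule in 8.3.

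**Working it through.** **Inputs.** From 8.2: difference 0.53 SD, two-sided alpha 0.05, ICC 0.01, attrition 15%, 118 dyads before adjustment, 140 enrolled. From 1.1: 148 enrolled. From 3.1 and 5.2: 18 visitors, 9 per arm. The 16 degrees of freedom follow from the last item and are not written in the plan.

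**Formula.** With N completers, DE = 1 + (N/18 − 1) × 0.01, and the noncentrality is 0.53 × √(N / (4 × DE)). Power comes from the noncentral t distribution.

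**Step 1: reproduce the plan's figure.** For 118 independent dyads, the noncentrality is 0.53 × √(118/4) = 2.879. With 116 degrees of freedom power is 81.5%, in line with the stated 80%.

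**Step 2: add the design effect, then the degrees of freedom.**

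| | 140 enrolled | 148 enrolled |
|---|---|---|
| Completers (× 0.85) | 119 | 125.8 |
| Per visitor | 6.61 | 6.99 |
| DE | 1.0561 | 1.0599 |
| Noncentrality | 2.813 | 2.887 |
| Power, dyad-level df (N − 2) | 79.7% | 81.7% |
| Power, 16 df | 75.2% | 77.4% |
| Detectable effect at 80% power, 16 df | about 0.56 SD | about 0.55 SD |

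The loss from the reference distribution alone is 79.7 − 75.2 = 4.5 points, or 81.7 − 77.4 = 4.3 points. For scale only: 80% power at 16 degrees of freedom needs about 136 completers, and 136/0.85 = 160 enrolled.

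**Step 3: the mixed model that the plan names.** I simulated a balanced model with a visitor random effect and its variance truncated at zero, at ICC 0.01. The visitor variance is estimated as zero in about 47% of runs.

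| | 140 enrolled | 148 enrolled |
|---|---|---|
| Power, Satterthwaite-type df | about 74% | about 76% |
| Power, residual df | about 77% | about 79% |
| Type I error, Satterthwaite-type df | about 3.9% | about 3.9% |
| Type I error, residual df | about 4.4% | about 4.4% |

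So 75% and 77% describe a cluster-level test with 16 degrees of freedom. The Satterthwaite-type mixed model is about one point lower.

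**Step 4: larger ICCs (an assumption; the documents give only 0.01).** With residual degrees of freedom the type I error is about 5.4% to 5.5% at ICC 0.05 and about 6.0% to 6.5% at 0.10 to 0.20. With Satterthwaite-type degrees of freedom it is at most 5.0% across ICCs from 0.01 to 0.20.

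**Step 5: where 140 and 148 come from.** 118/0.85 = 138.8, which leads to 140 with no inflation factor. With m = 118/18 = 6.56 the factor is 1.0556; 118 × 1.0556 = 124.6, and 124.6/0.85 = 146.5, close to 148. Another route to 140 exists: 112 × 1.0522 = 117.8, and 117.8/0.85 = 138.6. The text does not show which was taken.

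**The case against.** *The plan already handles clustering.* This is right as far as it goes. A reader might infer from 118 dyads and a plain t-test that the trial was powered as if dyads were independent. The documents do not support that: 8.2 calls 118 unadjusted, gives a design effect and states an ICC. The arithmetic in step 5 suggests that the factor may not have entered the 140, but the second route to that number keeps this from being conclusive. In any case the variance side costs little, since power with the design effect alone is about 80% to 82%.

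*The 16 degrees of freedom are not in the plan.* True. They follow from randomising 9 + 9 visitors, and the conclusion should be stated on that basis.

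*At the planned ICC, residual degrees of freedom are acceptable.* This stands. A reader might infer that the planned test is too liberal. At ICC 0.01 it is not (about 4.4%), and with 148 enrolled its power of about 79% is close to the stated figure. Inflation appears only at larger ICCs. The secondary outcomes that visitors teach directly might have such ICCs, but no document says so.

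*Covariate adjustment will recover the loss.* If covariates explained 5% to 10% of the variance in weight change (an assumption), power at 16 degrees of freedom would be 77.3% to 79.5% with 140 and 79.4% to 81.5% with 148. But the power stated in 8.2 is for an unadjusted comparison, and the documents give no figure for explained variance. This does not rescue the stated 80%.

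**Conclusion.** The point holds as a modest overstatement of power and an unspecified analysis detail. On the plan's effect size, ICC and attrition, and 16 degrees of freedom inferred from 18 randomised visitors, power is about 75% (140 enrolled) or 77% (148) for a cluster-level test. For a mixed model with Satterthwaite-type degrees of freedom it is about 74% or 76%. Nearly all of the shortfall comes from the reference distribution, not from ignored clustering.

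These figures assume equal caseloads. With a coefficient of variation in cluster size of 0.4 to 0.6 (an assumption), the 16-df power falls to 74.3% to 74.8% with 140 and to 76.4% to 76.9% with 148. The model structure in 8.3 is sound, and the detectable effect moves only from 0.53 to about 0.55 or 0.56 SD. This is a minor correction, worth making because it is cheap.

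**What to change.** - In 8.3.1, name Kenward-Roger or Satterthwaite degrees of freedom for all arm effects, primary and secondary. A cluster-level test with 16 degrees of freedom is an acceptable alternative.
- In 8.2, restate power for whichever test is named, at 0.53 SD, ICC 0.01, 15% attrition and 18 visitors: about 74% (140) or 76% (148) for the Satterthwaite-type mixed model, or about 75% or 77% for the 16-df cluster-level test.
- Reconcile the 140 in 8.2 with the 148 in the synopsis, and show the step at which the inflation factor is applied.

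The cost is one model option and a revised sentence or two, with a stated power slightly less favourable than 80%. No change in enrolment is needed.

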8.3.2 ANALYSIS OF THE PRIMARY ENDPOINT(S)

For the primary endpoints, weight of mother or child between baseline and the 6-month and 12-month timepoints will be calculated and summarized by tabulating and plotting descriptive statistics by the study arms. Linear association of HABITS with weight changes will be estimated and adjusted for demographic

information and other measured covariates by performing mixed regression models with home visitors as a random effect.

8.3.3 ANALYSIS OF THE SECONDARY ENDPOINT(S)

For the secondary endpoints, the analyses approach planned for primary endpoints will be used for determining if HABITS is associated with changes in maternal feeding practices, habit strength of targeted behaviors, or the household environments between baseline and 6- or 12-month follow-up.

8.3.4 SAFETY ANALYSES

Rates and severity of adverse events will be summarized using descriptive statistics and compared between study arms by Chi-square test of equal proportions.

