7.2.3 CLASSIFICATION OF AN ADVERSE EVENT

7.2.3.1 SEVERITY OF EVENT

For adverse events (AEs), the following guidelines will be used to describe severity:

- **Mild** – Events require minimal or no treatment and do not interfere with the subject's daily activities.
- **Moderate** – Events result in a low level of inconvenience or concern with the therapeutic measures. Moderate events may cause some interference with functioning.
- **Severe** – Events interrupt a subject's usual daily activity and may require systemic drug therapy or other treatment. Severe events are usually potentially life-threatening or incapacitating. Of note, the term "severe" does not necessarily equate to "serious."

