8.3 STATISTICAL ANALYSES

At each time of measurement, descriptive statistics and measures of association will be used to summarize demographic characteristics and outcome measures. The analysis will also include graphical and statistical analysis of outlying observations and distributional characteristics of variables. Differences in outcomes of interest between the control and HABITS will be assessed by t-test of equal means and Chi-square test of equal proportions for continuous, ordinal, and categorical values, respectively.

For hypothesis 1 (primary outcomes), weight of mother or child between baseline and the 6-month and 12-month timepoints will be calculated and summarized by tabulating and plotting descriptive statistics by the study arms. Linear association of HABITS with weight changes will be estimated and adjusted for demographic information and other measured covariates by performing mixed regression models with home visitors as a random effect.

For hypothesis 2 (secondary outcomes), the analyses approach planned for Aim 1 will be used for determining if HABITS is associated with changes in maternal feeding practices, habit strength of targeted behaviors, or the household environments between baseline and 6- or 12-month follow-up.

Missing data will be addressed using multiple imputation and/or full information maximum likelihood estimation. Psychometric properties of the study scales will be investigated to ascertain appropriate validity and reliability. All statistical analyses will be performed using the most current version of SAS 9.4. Final results will be determined to be statistically significant when the accompanying statistical test yields a two-tailed probability of 0.05 or less.

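### Adverse event severity is an ordered scale, but its only between-arm test is a chi-square of equal proportions, which ignores the order of the grades and the home-visitor clusters

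*Combined protocol and SAP*

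**What the plan says.** Section 7.2.3.1 introduces the severity scale with "For adverse events (AEs), the following guidelines will be used to describe severity" and then defines mild, moderate and severe, in increasing order.

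Section 8.3.4 is one sentence: "Rates and severity of adverse events will be summarized using descriptive statistics and compared between study arms by Chi-square test of equal proportions". It does not say whether the table counts events or participants, whether it spans all grades, or whether clustering is allowed for. No trend, rank or ordinal-model test is named anywhere in the document.

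For efficacy, Section 8.3.1 says: "Primary and secondary outcomes will be assessed using mixed regression models with home visitors as a random effect". That sentence covers primary and secondary outcomes, not adverse events.

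Sections 8.3, 8.3.1 and 8.3.5 also carry a general rule for between-arm comparisons: "t-test of equal means and Chi-square test of equal proportions for continuous, ordinal, and categorical values, respectively". It names two tests for three data types.

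Significance is two-sided at 0.05 (Section 8.3).

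**The concern.** The safety question is whether events under HABITS are shifted towards worse grades. A chi-square test across the grades treats them as unordered labels: shuffle mild, moderate and severe and the p-value stays the same. Its degrees of freedom are spread over every possible pattern of difference, so it has less power for a shift than a one-degree-of-freedom test that uses the order.

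Home visitors are the randomized units (Section 5.2), and the efficacy models carry a home-visitor random effect. The severity test carries none. Section 7.2.4 also asks for each intermittent episode and each change in severity to be documented, so one participant can supply several records. If events were tabulated, the test would treat those records as independent.

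At stake is the sensitivity and validity of the one planned comparison of severity. The primary and secondary conclusions do not depend on it.

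**Working it through.** **1. The plan's own power figure.** Section 8.2 gives the only one, for weight change: "A sample size of 59 dyads per group, total of 118 dyads, will have 80% power to detect" a difference of "0.53 standard deviation". A two-sample t-test at two-sided 0.05 needs 56.9, so 57 per arm, for 80% power. At 59 per arm the power is 81.5%. The figure is reproduced closely enough to use 59 per arm as the working size. No power is stated for adverse events.

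**2. Large-sample ceiling.** Give both tests the same noncentrality λ, which is the case when the difference lies wholly in the ordered direction. With k levels the chi-square has k − 1 degrees of freedom and the ordered test has 1:

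loss(λ) = P[χ²₁(λ) > 3.84] − P[χ²ₖ₋₁(λ) > c], where c is the 5% critical value on k − 1 df.

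- k = 3: largest loss 10.5 points (62.8% v 52.2%, at λ = 5.2). When the ordered test has 80% power, chi-square has 70.9%, a loss of 9.1 points.
- k = 4: largest loss 17.0 points (66.3% v 49.3%, at λ = 5.7).
- k = 5: 21.8 points. k = 7: 28.7 points.

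**3. Simulation.** Assumptions: the control distributions shown, a proportional-odds shift to worse grades, independent records, and one record per participant. The ordered test is the Wilcoxon (row-mean-score) test with midranks. There were 20,000 trials per case. Power at 59 per arm, chi-square v rank test:

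| Control distribution (%) | OR 1.5 | OR 2 | OR 2.5 | OR 3 |
|---|---|---|---|---|
| 60/30/10 (three grades) | 15.4 v 20.0 | 39.4 v 49.9 | 63.5 v 74.2 | 79.9 v 87.7 |
| 70/25/5 (three grades) | 13.8 v 18.5 | 35.6 v 45.5 | 58.7 v 69.1 | 76.8 v 84.8 |
| 70/18/9/3 (none to severe) | 11.0 v 18.6 | 29.9 v 46.1 | 52.5 v 70.2 | 71.7 v 85.9 |
| 50/30/15/5 (none to severe) | 14.0 v 22.1 | 36.6 v 52.6 | 60.4 v 76.9 | 77.1 v 89.6 |

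- Three grades: over 30, 59 and 70 per arm the loss ran from 2.6 points (30 per arm, 60/30/10, OR 1.5) to 11.8 points (30 per arm, 70/25/5, OR 3). The top value passes the 10.5-point ceiling because of small-sample effects. In that setting chi-square rejected only 3.5% of the time under the null.
- Four levels, 59 per arm: 7.6 to 17.8 points.

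An independent repeat with 40,000 trials per case at 30 and 59 per arm agreed to within about 1 point.

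**4. A difference that does not follow the order.** With 60/30/10 v 60/10/30 at 59 per arm, chi-square has 90% power and the rank test 14%.

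**5. Size of the clustering omission.** With 118 dyads and 18 home visitors, m = 118/18 = 6.56. With the plan's ICC of 0.01, the inflation factor is 1 + (6.56 − 1) × 0.01 = 1.056. That ICC is not specific to adverse events, and the documents give none that is.

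**6. The ordinal rule.** The sentence in Sections 8.3, 8.3.1 and 8.3.5 pairs two tests with three data types one for one, which cannot be done. If ordinal values go to chi-square, the order is lost. If they go to the t-test, it is used: the linear-trend test stayed within about 3 points of the rank test in every shift case.

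**The case against.** **The test may not be what it seems.** Section 8.3.4 does not say that the chi-square spans all grades. It might compare a single proportion, such as participants with a severe event. The power comparison above would not apply to such a test. This stands, and the finding is conditional on a test across the grades.

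**An omnibus test is defensible for safety.** It can detect a pattern nobody predicted, and step 4 shows the advantage can be large. This also stands as a real cost of switching, and it is the reason to keep the grade-by-arm table.

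**The stakes are modest.** The protocol calls the intervention low-risk (Section 2.3.1), no safety hypothesis is powered, and descriptive summaries are planned alongside the test. Nothing in the plan says that a non-significant result will be reported as no difference.

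**The inputs are assumed.** True: the documents give no event rates, severity split or expected effect. With few events both tests have little power and the absolute loss shrinks.

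**A larger claim is tempting.** A reader might infer a loss of 10 to 30 points for severity, or that ordinal study outcomes are tested by chi-square alone. The documents support neither. About 10 points is roughly the ceiling for three grades and 17 for four. Losses of 20 to 30 points need scales of about five to seven levels. Chi-square for ordinal outcomes is only one reading of an ambiguous sentence, and primary and secondary outcomes are assigned to mixed models as well.

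**Conclusion.** The point holds for adverse event severity. The plan's only between-arm test of an ordered scale does not use the order if it is run across the grades, and it makes no allowance for the randomized unit. Against a consistent shift to worse grades, the cost is about 3 to 12 points of power with three grades tabulated. It is about 8 to 18 points at 59 per arm with worst grade scored none/mild/moderate/severe. Both ranges assume independent records, a proportional-odds shift with odds ratios of 1.5 to 3, and assumed grade distributions. The behaviour of a cumulative-logit mixed model with 18 home visitors and few severe events was not simulated.

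For ordinal values in Sections 8.3, 8.3.1 and 8.3.5, the supported finding is ambiguity about which test applies. No power loss should be claimed there for the study outcomes.

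**What to change.** **Section 8.3.4.** State the unit of analysis. Keep the grade-by-arm table, and keep chi-square for unordered proportions only. Compare each participant's worst grade (none, mild, moderate, severe) between arms with a cumulative-logit model that allows for home-visitor clustering, for example a random effect in SAS PROC GLIMMIX. Report the odds ratio with its confidence interval.

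If events are too sparse for that model, use the rank (row-mean-score) statistic with a permutation p-value obtained by reallocating home visitors. An ordinary Cochran-Mantel-Haenszel test is not a substitute, because it ignores clustering. Stratifying it by home visitor cannot help, since each visitor belongs to one arm. With 9 of 18 visitors per arm there are 18!/(9! × 9!) = 48,620 possible allocations if randomization was unrestricted, so the permutation test is practical.

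**Sections 8.3, 8.3.1 and 8.3.5.** Name one test per data type: t-test for continuous values, an order-using test for ordinal values, and chi-square for unordered categories.

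**Cost.** A few sentences and one standard procedure, with no new data or participants. There are two downsides. The ordinal test is less sensitive to a difference that does not follow the order. The four-level score also merges occurrence with severity, so the proportion with any event should still be reported separately.

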8.3.5 BASELINE DESCRIPTIVE STATISTICS

At baseline, descriptive statistics will be used to summarize demographic characteristics and outcome measures by study arm and for the entire sample. The analysis will also include graphical and statistical analysis of outlying observations and distributional characteristics of baseline descriptive variables. Differences in baseline characteristics of interest between the control and HABITS will be assessed by t-test of equal means and Chi-square test of equal proportions for continuous, ordinal, and categorical values, respectively.

9 SUPPORTING DOCUMENTATION AND OPERATIONAL CONSIDERATIONS

9.1 REGULATORY, ETHICAL, AND STUDY OVERSIGHT CONSIDERATIONS

9.1.1 INFORMED CONSENT PROCESS

9.1.1.1 CONSENT/ASSENT AND OTHER INFORMATIONAL DOCUMENTS PROVIDED TO SUBJECTS

Consent forms describing in detail the study intervention, study procedures, and risks are given to the subject and written documentation of informed consent is required prior to conducting study screening procedures. A separate screening consent form will not be used.

9.1.1.2 CONSENT PROCEDURES AND DOCUMENTATION

Informed consent is a process that is initiated prior to the individual's agreeing to participate in the study and continues throughout the individual's study participation. Consent forms will be Institutional Review Board (IRB)-approved and the subject will be asked to read and review the document. The investigator will explain the research study to the subject and answer any questions that may arise. A verbal explanation will be provided in terms suited to the subject's comprehension of the purposes, procedures, and potential risks of the study and of their rights as research subjects. Subjects will have the opportunity to carefully review the written consent form and ask questions prior to signing. The subjects should have the opportunity to discuss the study with their family or surrogates or think about it prior to agreeing to participate. The subject will sign the informed consent document prior to any procedures being done specifically for the study. Subjects must be informed that participation is voluntary and that they may withdraw from the study at any time, without prejudice. A copy of the

informed consent document will be given to the subjects for their records. The informed consent process will be conducted and documented in the source document (including the date), and the form signed, before the subject undergoes any study-specific procedures. The rights and welfare of the subjects will be protected by emphasizing to them that the quality of their medical care will not be adversely affected if they decline to participate in this study.

